BIOSCIENCE INSTRUCTIONS AND TEMPLATE

NUMBER	DATE	PAGE
HRP-503b	3/31/2020	1 of 4

1 Protocol Title

Community Pharmacists Vaccinating Against Cancer (CPVAC): A Pilot Randomized Controlled Trial Aimed at Increasing HPV Vaccine Completion Rates Among Racially/Ethnically Diverse Youth

2 Background and Objectives

The majority of HPV-related cancers and genital warts can be prevented through the timely uptake and completion of the HPV vaccine series.^{23,25,26} Human papillomavirus (HPV) is the most common sexually transmitted infection, and persistent infection with oncogenic HPV strains cause cancer.²⁷ The HPV strains most commonly associated with cancer are HPV 16 and 18. However, strains 31, 33, 35, 39, 45, 51, 52, 56, 58, and 59 are also carcinogenic.²⁸ Commercially available 9-valent HPV vaccines offer the potential of immunity against seven oncogenic strains (Types 16, 18, 31, 33, 45, 52, 58) and the two low-risk strains (Types 6 and 11) that cause over 90% of genital warts.²⁹ Vaccine completion is critical because it boosts the body's ability to fight off the virus.³

In 2016 only 37.5% of HPV vaccine age-eligible males and 49.5% of females completed the HPV vaccine series⁷ with racial/ethnic minorities exhibiting lower rates of completion.⁸ Specifically, Black and Latino children and young adults have a higher rate of initiation of the vaccine;⁹ however, they have a significantly lower likelihood of completing the vaccine series.⁹ Further, Latino patients who prefer speaking Spanish as opposed to English have lower HPV vaccine completion rates.¹⁰ It is critical to enhance HPV vaccine series completion among racial/ethnic minority HPV vaccine age-eligible individuals to reduce cancer disparities. Barriers to complete the HPV vaccine have included the following: lack of time to receive the follow-up vaccines,¹¹ transportation needed to return for follow-up clinical visits,¹¹ additional office co-pays,³¹ lack of awareness to receive additional HPV vaccine doses,³² and Lack of strong provider recommendation for vaccine initiation/completion³⁴ particularly for male patients.

Traditionally, primary care providers (PCPs) administer all HPV vaccine doses. After individuals receive the first HPV vaccine dose from their PCP, they must return to their primary care clinic for additional doses. This places a burden on patients and their caregivers to schedule and attend additional, non-routine clinical visits.¹¹⁻¹³ However, PCPs are not the only providers who can administer the HPV vaccine. Pharmacists can administer additional vaccine doses.^{14,15} Receiving additional vaccine doses with pharmacists may prove to be a more convenient method of ensuring vaccine adherence due to pharmacies' extended hours (compared to PCP clinics) and lack of required appointment.¹⁶⁻¹⁸ Many have built-in text-message reminder systems, which increase vaccine adherence¹⁹ by prompting patients to return to the pharmacy when medication (vaccine dose) has been filled. Although numerous studies describe the potential for pharmacists to aid in HPV vaccine series completion, few, if any, intervention research studies have actually tested this integrated model of care.²⁰⁻²⁴

Therefore, we propose to pilot and test a theoretically-informed (Diffusion of Innovation) integrated intervention model that we call CPVAC (Community Pharmacists Vaccinating Against Cancer). CPVAC will be a randomized controlled pilot intervention. Caregivers of patients who complete the initial HPV vaccine will be asked to take part in the study. The PI will recruit a stratified sample of patients, oversampling for Latino (English and Spanish speakers) and African American patients. Patients will be randomized to intervention or control group (usual care). After enrolling in the study, primary care providers of patients in the Intervention Group will contact the patients' community pharmacy (e.g. CVS, Walgreens, Fry's) and prescribe the remaining HPV vaccine dose(s). The pharmacy will electronically update patients' files and schedule the HPV vaccine "refill" (additional doses) at the appropriate dosing schedule. The pharmacy will contact patients or (for minors) patients' caregivers when it is time to complete additional HPV vaccine dose(s). Control group participants will receive usual care, returning to their PCPs to complete the additional HPV vaccine series.

3 Data Use

Data will be published in peer-reviewed journals and presented at academic conferences. Results will be released to Adelante Healthcare Mesa, the site for this research study.

4 Inclusion and Exclusion Criteria

Inclusion Criteria	Exclusion Criteria
Caregivers of a child between ages 9-18 who has either not received any HPV vaccine doses or has received only initial HPV dose	Caregivers whose child has completed additional HPV vaccine doses
Receives care at Adelante Healthcare Mesa	
Fluent in English and/or Spanish	
Willing to provide informed consent	

BIOSCIENCE INSTRUCTIONS AND TEMPLATE

NUMBER	DATE	PAGE
HRP-503b	3/31/2020	2 of 4

5 Number of Participants

90 participants will be enrolled in the study; 45 in the control group / 45 in the intervention group

6 Recruitment Methods

The study research assistants (RA) will work directly with the clinic during the study enrollment period to generate a list of all patients (and their caregivers) who may be eligible to participate in the study. Adelante office staff will search patients' online medical files to determine which individuals are age-eligible for the vaccine who have either 1) not initiated the vaccine series and/or 2) have only completed one of the HPV vaccine doses. They will generate a list of eligible patients with caregiver contact information to the RA.

The RA will use a vacant office space for all recruitment and enrollment activities. To initiate contact with potential participants, she will send a letter to caregivers of children eligible for HPV vaccine, inviting them to take part in a study about HPV vaccine intentions. The letter will contain study-specific phone number that will reach RA's office directly. RA will screen caregivers for eligibility and notify clinic staff of all patients/caregivers eligible for study. Caregivers will work with clinic staff to schedule an office visit. When the clinic staff schedules the patient's visit, they will ask caregivers to stay an addition 15-20 minutes after their scheduled appointment to complete the study informed consent and baseline surveys.

7 Study Timelines

We anticipate participants being a part of the study for up to 8 months. We expect that individuals will spend up to 2 hours (1 hour on 2 days) on completing study surveys, one on the first day of the study and another after six months. They will also spend time taking their child to receive the additional HPV vaccine doses.

8 Procedures Involved

The project utilizes a software (REDCap) which randomizes individuals into intervention and control groups, using permuted block randomization. As participants enroll in the study, they will be given a study identification number (e.g. 1,2,3). Both the intervention and control groups will complete baseline surveys.

Control group participants will receive standard care and will be expected to return to Adelante Healthcare Mesa to receive the additional HPV vaccine booster doses. Intervention group participants will be referred to receive the additional HPV vaccine doses at their community pharmacy. At post-intervention, intervention participants will be asked if their children completed the HPV vaccine series.

Primary behavioral outcome: At the end of the 16-month intervention, PI will ask clinic staff to report HPV vaccination dose completion (for vaccine doses 1,2,3) for all study participants.

Follow-up Survey Data Collection: RA will call all participants and administer follow-up survey to measure potential changes in DOI theoretical constructs (see baseline survey).

Qualitative telephone in-depth interviews: To qualitatively explore intervention feasibility and acceptability, PI will conduct telephone interviews with patients, patients' caregivers, clinic primary care providers, and clinic pharmacists.

- In-depth interview with Caregivers and/or Young Adult Patients: PI will conduct telephone interviews with caregivers from the control group (standard care) and from the intervention group (pharmacist-administered HPV vaccination) related to their experiences taking part in the study.
- In-Depth interviews with Providers and Pharmacists: Researchers will conduct telephone interviews with all the clinic's participating primary health care providers and office manager (n= 4) and local pharmacists who work at pharmacies where patients were referred to receive the HPV vaccine (n=4) to explore their acceptability and perceived feasibility of the intervention. They will be asked how the intervention impacted the quality of patient care, ways in which the intervention impacted patient flow within the clinic, how satisfied they were with the intervention, and perceived fit of the intervention within their workplace.

Participant Incentives: Research participants will receive e-gift card incentives (of their choosing from Tango Card, Inc) for completing study surveys (\$20 dollars per survey completed) and for participating in telephone interviews (\$30).

9 Withdrawal of Participants

There are no anticipated circumstances under which participants will be withdrawn from the research study without their consent.

If participants choose to no longer take part in this study, they are asked to contact the PI ([name], [contact]) to notify her that they will no longer be involved in the study. The PI will remove and destroy all participant data from the study.

BIOSCIENCE INSTRUCTIONS AND TEMPLATE

NUMBER	DATE	PAGE
HRP-503b	3/31/2020	3 of 4

10 Risks to Participants

There are no foreseeable risks to research participants. Risks of the HPV vaccine (a non-virus vaccine –which utilizes a protein which looks similar to HPV) include a fever, pain at injection site, and a headache. A much less common side effect of the vaccine is fainting within 15 minutes of injection. For this reason /risk, patients are told to remain at the clinic/pharmacy for an additional 15 minutes after they receive the vaccine to ensure that they are safe to leave.

11 Potential Benefits to Participants

HPV vaccine age-eligible children will complete the HPV vaccine series, thus preventing the risk of HPV-related cancers. Also, intervention participants will learn more about the role of the community pharmacist in administering vaccines and vaccine booster doses. This may help aid in the completion of vaccine series without having to schedule and revisit primary care providers' offices.

12 Setting

This study will be conducted at Adelante Healthcare Mesa, a local federally qualified health center. Intervention participants will be referred to receive additional HPV vaccine booster shots with their community pharmacists. Pharmacists are currently licensed to administer the HPV vaccine.

13 Multi-Site Research

NA

14 Resources Available

This clinically based study will take place at Adelante Healthcare Mesa, a Federally Qualified Health Center (FQHC) which predominantly serves ethnic/racial minority, low-income populations.

15 Prior Approvals

We have received prior approval and secured an MOU with Adelante Healthcare Mesa to conduct this study.

16 Data Management and Confidentiality
Data Analysis:
Aim 1 Data Analysis: Assessing Preliminary Efficacy.

The specific aim of the proposed project is to investigate the effect of CPVAC on HPV vaccination completion rate compared with primary care provider (Aim 1).

Patient-related outcomes: Two proportion Z tests will be used to examine the proportion differences in HPV vaccination completion between CPVAC and primary care provider (PCP) groups. We will also compare which medical professionals completed the vaccine doses. We will create codes for various health care professionals (e.g. nurse, nurse practitioner, physician, pharmacist, etc.) to differentiate who administered the vaccine. The HPV completion status will be classified as dichotomous variable (0 = no; 1 = yes). Independent variables will be classified as either categorical or continuous scale: age, gender, race; location, HPV vaccine dose (1, 2, 3, etc); provider types (PCP vs pharmacist); facility type/place of service (health clinic vs. pharmacy). Multiple logistic regression with stepwise selection procedures will be used to identify whether these independent variables are associated with HPV completion status.

Psychosocial Constructs Data Analysis: Baseline characteristics of the study participants will be summarized using descriptive statistics. Multiple logistic regression will be used to investigate whether psychosocial factors (e.g. intention, norms, efficacy) relate to HPV vaccine completion (yes/no). General linear models or Mann-Whitney U tests will be used to test mean or median differences for self-efficacy and response-efficacy to complete the vaccine series between CPVAC and PCP groups.

Missing Data: We will conduct sensitivity analyses including imputation methods and completer-only analyses. All statistical procedures and analyses will be performed in SPSS software.

BIOSCIENCE INSTRUCTIONS AND TEMPLATE

NUMBER	DATE	PAGE
HRP-503b	3/31/2020	4 of 4

Aim 2 Data Analysis: Qualitatively exploring feasibility and acceptability of CPVAC

PI will submit the interview audio-recordings to an ASU-approved transcription company. Using the interview guide to determine a priori themes, PI will create a coding book for the interview data. Reading through all interview transcripts, PI will add emerging themes to expand the coding guide. PI will train the RA in descriptive content analysis. They will review and code one transcript together, code an additional three transcripts separately, meet to discuss coding choices, and reach an agreement on data interpretations and analysis before they split the remaining interview transcripts for review. PI and RA will upload all transcripts and codes into ATLAS.ti software. PI will take the outcomes from the analyses from ATLAS.ti and begin to summarize findings for each in-depth interview question with the RA to ensure interpretation consensus and create a comprehensive summary of the findings related to intervention acceptability and feasibility.

Data Storage:

Patients' information will be de-identified and given a unique Participant Study Number for data analysis by an Adelante Healthcare Mesa healthcare practitioner. All signed informed consent documents will remain with the PI. She will secure them in a locked drawer of a locked office. These forms will be kept up to two years and will be destroyed at the end of those two years.

17 Safety Monitoring

[name] (PI) and the research assistants will meet on a monthly basis to evaluate the data collected for the study. They will review completeness of patient surveys and informed consent and updates related to HPV vaccine series completion.

18 Consent Process

The clinic will notify the RAs when potential participants have scheduled office visits. After the office visit, a nurse or office staff member will walk the patient to the RA's research office. The RA will briefly explain that this study is about HPV vaccine intentions and vaccine completion and invite caregivers to sign up for the study. If patients decide not to sign up that day, they will be given a study information sheet and a phone number to call should they decide to participate later. RA will also write down their contact information to follow up on study enrollment. For caregivers interested in signing up for the study, the RA will administer the informed consent and baseline surveys.

The project biostatistician will have already generated a randomization table for the intervention and control groups, using permuted block randomization. As participants enroll in the study, they will be given a study identification number (e.g. 1,2,3). Based on their study number and the randomization table, they will be assigned to either intervention or control group.

For the in-depth interviews with caregivers (at post-intervention), the RA will contact participants via phone. The RA will administer informed consent via the phone and verbally consent participants prior to conducting the phone interviews.

19 Investigational New Drug or Devices

NA

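### The promised oversampling by ethnicity and language has no recruitment mechanism, and the arm comparison adjusts for neither factor although the protocol links both to completion

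*Combined protocol and SAP*

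**What the plan says.** **Sampling.** Section 2 (Background and Objectives) commits to this: "The PI will recruit a stratified sample of patients, oversampling for Latino (English and Spanish speakers) and African American patients". No group sizes, quotas or sampling fractions follow.

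**Why these groups matter.** Section 2 says of Black and Latino children and young adults: "however, they have a significantly lower likelihood of completing the vaccine series". It adds: "Latino patients who prefer speaking Spanish as opposed to English have lower HPV vaccine completion rates". It does not give the size of either gap.

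**Recruitment.** Under Section 6, research assistants work with the clinic to "generate a list of all patients (and their caregivers) who may be eligible to participate in the study". The search behind the list is described as: "Adelante office staff will search patients' online medical files to determine which individuals are age-eligible for the vaccine who have either" not started the series or received one dose only. Caregivers are then sent a letter and telephone in. Race, ethnicity and language play no part in these steps. Section 4 uses fluency in English and/or Spanish only as an eligibility criterion.

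**Allocation.** Section 5 states: "90 participants will be enrolled in the study; 45 in the control group / 45 in the intervention group". Section 8 allocates "using permuted block randomization", and Section 18 assigns by study number from a randomisation table. Neither names a stratification factor or a block size.

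**Analysis.** Section 16 compares completion between arms with two-proportion Z tests. A separate logistic regression with stepwise selection has this list: "Independent variables will be classified as either categorical or continuous scale: age, gender, race; location", followed by vaccine dose, provider type and facility type. Treatment arm and language are not on it.

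**The concern.** There are two separate gaps.

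The first is an inconsistency within the protocol. Section 2 promises a particular mix of participants, and Section 6, the operational section, contains no step that would produce it. The title names racially and ethnically diverse youth, so too few participants from the named groups would undercut the stated purpose.

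The second is a missed opportunity in the analysis. The protocol identifies ethnicity and language as related to the primary outcome. With 45 per arm these factors can fall unevenly by chance, and the only between-arm test cannot take that into account. The stepwise regression does not fill the gap. It searches for predictors, may drop race, has no language variable and, as listed, does not estimate the effect of assigned arm. At stake are some precision and the ability to answer a reader who sees an uneven baseline table.

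**Working it through.** **Inputs from the documents:** 90 participants, 45 per arm (Section 5); background completion of 37.5% in males and 49.5% in females (Section 2).

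**Assumptions, because the documents give no figures:** a stratum of 20 of the 90 participants; a completion gap of 15 to 30 points between that stratum and the rest; two-sided alpha of 0.05 and 80% power where power is mentioned.

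The plan gives no calculation behind the 90, so the only check on it is 45 + 45 = 90.

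**Step 1: chance of imbalance without stratification.** Let X be the number of the 20 who fall in one arm. With 45 of 90 allocated to each arm, X is hypergeometric (population 90, stratum 20, draw 45).
- P(12:8 or worse, either direction) = 1 − P(9 ≤ X ≤ 11) = 44.7%.
- P(13:7 or worse, either direction) = 1 − P(8 ≤ X ≤ 12) = 20.4%.

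Simulated unstratified blocks of 2, 4 or 6 give about 44–45% and 20–21%, so the unstated block size hardly matters.

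**Step 2: other stratum sizes.** P(arms differ by at least 10 / 15 / 20 percentage points in the stratum's share), hypergeometric:

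| Stratum share | ≥10 points | ≥15 points | ≥20 points |
|---|---|---|---|
| 20% (18 of 90) | 18.7% | 6.3% | 1.6% |
| One third (30 of 90) | 26.3% | 11.7% | 4.3% |
| One half (45 of 90) | 39.9% | 20.6% | 9.1% |

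**Step 3: shift in the arm difference.** Shift = (difference in stratum share) × (completion gap).
- 13:7 split: (13 − 7)/45 = 0.133. Times 15 points = 2.0; times 30 points = 4.0.
- Typical draw: SD of X = √[45 × (20/90) × (70/90) × (45/89)] = 1.98. SD of the share difference = 2 × 1.98/45 = 0.088. Times 15 to 30 points = 1.3 to 2.6 points.

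**Step 4: scale.** Standard error of the difference = √[2p(1 − p)/45].
- p = 0.375: √(2 × 0.375 × 0.625/45) = 0.102.
- p = 0.495: √(2 × 0.495 × 0.505/45) = 0.105.

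So it is about 10 points. From control rates of 37.5% to 49.5%, the difference detectable with 80% power is about 28 to 29 points.

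**Step 5: is the unadjusted test valid?** In simulations with blocks of 4, a stratum of 20, overall completion of 45% (assumed), no treatment effect and a gap of 15 or 30 points, the nominal 5% Z test rejected between 4% and 5% of the time. False positives are not inflated.

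**Step 6: what adjustment can gain.** Share of outcome variance explained by the stratum = f(1 − f)g²/[p(1 − p)], with f the stratum share and g the gap. With f = 20/90 and p = 0.45:
- g = 0.15: 0.1728 × 0.0225/0.2475 = 1.6%.
- g = 0.30: 0.1728 × 0.09/0.2475 = 6.3%.

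The gain is real but small.

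**The case against.** The other side has a good case on several points.

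- **Stratified sampling is not stratified randomisation.** Section 2 speaks of who is recruited. Unstratified permuted blocks contradict nothing there and are an accepted design for 90 participants. This stands, so stratified allocation is offered below only as an option.
- **A reader might infer that imbalance would confound or bias the comparison.** The documents do not support this. Allocation is random, so the Z test is unbiased on average and its standard error already covers such imbalance (Step 5). The 2 to 4 points is a shift conditional on an unfavourable draw that occurs about one time in five.
- **A reader might infer that the analysis ignores the groups altogether.** It does not: race is on the Section 16 list. As a stepwise candidate in a model without treatment arm, however, it does not adjust the arm comparison.
- **A reader might infer that the oversampling is meant to support estimates within groups.** No section plans any, and it may serve representation only. Harm to such estimates is no part of this point.
- **Small groups.** In a pilot of 90, some groups may be too sparse to adjust for separately. This is fair, and the fix allows for it.

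None of this answers the gap between Sections 2 and 6, or the absence of language from every analysis.

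**Conclusion.** The point holds as a minor one. Two parts rest on the text alone: Section 6 has no mechanism for the sample that Section 2 promises, and the Section 16 arm comparison leaves out factors that Section 2 links to the outcome, with language missing entirely.

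The size rests on assumed stratum sizes and completion gaps. Under those assumptions a noticeable imbalance is quite likely, but its effect is a few points against a standard error of about 10. It would seldom change the trial's conclusion. The case for acting is that the change costs almost nothing and that the trial must know each participant's group anyway to deliver the promised sample.

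**What to change.** 1. **Recruitment (Section 6).** Record ethnicity and preferred language on the clinic's list, state a target for each Section 2 group, and release invitation letters by group until the targets are met.
2. **Primary comparison (Section 16).** Prespecify an arm comparison adjusted for one ethnicity/language factor that is always kept and not chosen stepwise. Examples are a Mantel-Haenszel risk difference, or a model with arm and that factor forced in. Set in advance the rule for combining sparse groups. The unadjusted Z test can be reported alongside.
3. **Optional: allocation (Sections 8 and 18).** Stratify the REDCap permuted blocks by the same factor. Blocks of 4, for example, would cap the imbalance at 2 participants per stratum.

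**Cost.** Items 1 and 2 need a few sentences, two fields on a list that is being made anyway, and some extra handling of the mailing. Item 3 is a software setting; it may leave a few blocks unfilled and the totals slightly off 45/45. The sample size stays at about 90.

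### The primary outcome comes from clinic staff, but only the intervention arm is sent elsewhere for its doses and only that arm is stated to be asked about completion, so ascertainment could differ by arm

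*Combined protocol and SAP*

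**What the plan says.** Section 8 (Procedures Involved) defines the primary behavioral outcome by a single report, taken at one time: "PI will ask clinic staff to report HPV vaccination dose completion (for vaccine doses 1,2,3) for all study participants".

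The same section separates the arms by place of vaccination. Controls "will be expected to return to Adelante Healthcare Mesa to receive the additional HPV vaccine booster doses". For the other arm: "Intervention group participants will be referred to receive the additional HPV vaccine doses at their community pharmacy". It then adds a question for one arm: "At post-intervention, intervention participants will be asked if their children completed the HPV vaccine series". No matching sentence covers controls. A follow-up call does go to everyone, but its stated purpose is to "administer follow-up survey to measure potential changes in DOI theoretical constructs".

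Three other places bear on how pharmacy doses become known:
- Section 2 has the provider prescribe the later doses to the pharmacy, which then makes an electronic entry in the patient's file and schedules the refill.
- Section 16 (Aim 1 analysis) codes completion 0/1, compares arms by a two-proportion Z test, and plans codes for the type of professional who gave each dose and for clinic versus pharmacy as place of service. It lists imputation and completer-only analyses as sensitivity analyses for missing data.
- Section 17 has the study team look each month at news of series completion.

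**The concern.** The people who report the outcome work where control doses are given, not where intervention doses are meant to be given. A control dose enters the reporter's own chart as a matter of routine. A pharmacy dose must travel there, and the plan does not say how. Completion is a 0/1 variable with no stated rule for a child whose pharmacy record nobody saw, so an unseen dose could be entered as 0. It would then look like an observed failure, and the planned missing-data analyses would not touch it.

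The caregiver question works in the opposite direction. If a caregiver's answer can turn a 0 into a 1 in one arm only, the intervention arm gets a second chance to be counted as complete.

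Randomization protects against neither, because place of vaccination is the intervention. In a pilot whose first aim is preliminary efficacy, the main cost is a distorted effect estimate carried into the planning of a larger trial.

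**Working it through.** **Is there a stated route?** Set side by side, the three places listed above do not supply one. The section 2 sentence concerns scheduling the refill; it does not say that the file is the clinic's or that an administered dose is reported. The codes in section 16 and the monthly review in section 17 need pharmacy data but name no source. Nothing says that a control child who uses a pharmacy would be found in the same way.

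**How much could it matter?** The plan gives 45 per arm but no alpha, power or assumed rates, so there is no figure of its own to reproduce. What follows is an illustration.

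*Inputs from the document:* 45 per arm (section 5); completion of 37.5% (males) and 49.5% (females) in 2016 (section 2), used as control rates. *Assumed:* two-sided 5% pooled Z test; miss rate m of 10% or 20% for pharmacy completions; complete capture at the clinic; all intervention and no control completions at pharmacies, which is the allocation section 8 intends. Because section 2 says minorities complete less often, a control rate of 25% is added as a further assumption.

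*Formulas.* With no true effect and true rate p in both arms, the observed intervention rate is p(1 - m) and the spurious difference is -pm. The test statistic is Z = [(x_I - x_C)/45] / sqrt[p̄(1 - p̄)(2/45)], with p̄ = (x_I + x_C)/90. The chance of a false result against CPVAC is the sum of the binomial probabilities over all pairs (x_I, x_C) with Z < -1.96.

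| p | m | Observed intervention rate | Spurious difference (points) | False rejection against CPVAC |
|---|---|---|---|---|
| 37.5% | 10% | 33.75% | -3.75 | 5.8% |
| 37.5% | 20% | 30.0% | -7.5 | 11.8% |
| 49.5% | 10% | 44.55% | -4.95 | 6.3% |
| 49.5% | 20% | 39.6% | -9.9 | 14.6% |
| 25% (assumed) | 10% | 22.5% | -2.5 | 4.9% |
| 25% (assumed) | 20% | 20.0% | -5.0 | 8.7% |

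At the two documented rates, m = 0 gives 2.3-2.5%. In children, m = 20% is 45 × 0.375 × 0.2 = 3.4 to 45 × 0.495 × 0.2 = 4.5 missed completions.

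*With a true gain* of 30 points (assumed), the expected estimate is (p + 0.30)(1 - m) - p. At m = 10% this is 23.3 points (p = 37.5%) to 22.1 (p = 49.5%). At m = 20% it is 16.5 to 14.1. Power falls from 81-87% to 57-59% and to 26-33%.

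*If leakage is partly shared* (50% of intervention and 20% of control completions at pharmacies, assumed), the spurious difference is p(0.2 - 0.5)m: -1.1 to -1.5 points at m = 10% and -2.3 to -3.0 at m = 20%. False rejection is then about 3% and 4%.

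*Opposite direction.* Suppose the caregiver answer counted in the intervention arm only and a share f of non-completers were reported as complete. The observed rate would be p + (1 - p)f. At f = 10% the difference is +6.25 points (p = 37.5%) to +5.05 (p = 49.5%), with false rejection in favor of CPVAC of 8.4% to 6.4%. At f = 20% it is +12.5 to +10.1 points, with 21.2% to 14.9%.

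*Unknown instead of 0.* If only completers' records go unobtained, dropping them gives an intervention rate of (p - pm)/(1 - pm). At m = 20% this is 0.300/0.925 = 32.4% against 37.5% (-5.1 points), or 0.396/0.901 = 44.0% against 49.5% (-5.5 points). That is better than -7.5 and -9.9 but not zero, which is why bounds are also needed.

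**The case against.** The plan asks one source, at one time, about every participant, and does not confine clinic staff to doses given at the clinic. The codes for pharmacist-given doses and place of service make no sense unless the team expects pharmacy data, and in the intervention arm the prescribing provider knows which pharmacy was used. A working route may well exist and simply be unwritten. That stands, and it limits the point: a reader might infer that pharmacy doses will be lost, and the documents do not show that.

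Nor does anything say that the caregiver answer enters the Z test. A reader might infer that self-report is an outcome source in one arm; the text supports only the conditional. The survey instrument is not in the text reviewed, so a dose question to controls cannot be ruled out.

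Two further readings should be resisted. One is that the timelines conflict, since section 7 says "We anticipate participants being a part of the study for up to 8 months" while section 8 takes the outcome "At the end of the 16-month intervention". The first can be time per participant and the second the length of the study, so no contradiction is shown. The other is that the plan relies on completer-only analysis. It lists that analysis beside imputation, and both as sensitivity analyses.

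Finally, every miss rate, over-report rate and pharmacy share above is assumed. That is correct, and the calculations show only how sensitive the result would be. The all-or-none pharmacy split, though, is not an extreme scenario; it is the allocation as planned.

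**Conclusion.** The point holds as a gap in ascertainment that should be fixed, with medium confidence. Followed as written, the plan can find doses differently in the two arms: one reporter located where control doses are given, no stated path for pharmacy doses, and a completion question stated for one arm. Neither the direction nor the size of any bias can be derived from the documents. Under the intended allocation and full clinic capture, an assumed loss of 10% to 20% of pharmacy completions is enough to raise false rejection against CPVAC from a nominal 2.5% to about 6% and 12-15%, and to take roughly a quarter to a half off a true 30-point gain. If few doses are lost, or losses are shared between arms, the effect is small.

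**What to change.** 1. In both arms, count a dose if it is documented in the clinic chart or in a pharmacy record, with the same sources and the same cut-off for every child. If a pharmacy-to-clinic route already exists, state it and apply it to both arms.
2. Ask caregivers in both arms the same completion question: which doses, when and where. Use the answers to direct record checks, and use unverified self-report only in a sensitivity analysis covering both arms.
3. Code a child whose pharmacy record could not be obtained as unknown, not 0. Add bounds to the sensitivity analyses already planned, counting all unknowns as complete and then all as not complete. Each unknown child moves that arm's rate by 1/45, or 2.2 points.

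The cost is low: protocol wording, one more question to controls, and some pharmacy record requests, with a release if the consent form (not in the text reviewed) does not already cover it. One small downside is that asking controls where doses were given might prompt a few to use a pharmacy.
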